### F.2.2 Treatment failure

Inability to implant the Valiant Evo Thoracic Stent Graft System following arterial access due to deployment issues or entrapment of the delivery system will be considered a treatment failure. These subjects will be followed for 30 days and thereafter per institutional standard of care. Serious adverse events will be recorded in the eCRF until the total duration of the trial. At the end of the study the exit form should be completed.

If a primary conversion to open repair is required during the index procedure, then the subject will be followed for 30 days and thereafter per institutional standard of care. Serious adverse events will be recorded in the eCRF until the total duration of the trial. At the end of the study the exit form should be completed.

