## C.5 Study design

The Valiant Evo International Clinical Trial is a non-randomized, multicenter, open-label, prospective, single-arm trial. The trial is designed to assess the clinical safety and effectiveness of the Valiant Evo Thoracic Stent Graft System. A sample of 47 subjects will be included and evaluated for the 30-day primary endpoint. Data from these 47 subjects will be analyzed and used to support CE Mark approval. All subjects included will continue to be followed under this investigational protocol beyond the 30-day primary endpoint out to 12 months post-implantation. Subjects will have required follow-up evaluations at the following time points:

- 1-month following the index procedure
- 12-months following the index procedure

All subjects will be consented for up to 2 years of follow-up. This is to accommodate any global clinical investigational requirements, if required.

*Number of devices being used within this trial:*

For subjects that are treated with the Valiant Evo Thoracic Stent Graft a single, primary stent graft may be used by itself if its size is sufficient to provide the desired coverage. Alternatively, it may be used in combination with additional stent graft sections that increases the graft length distally or proximally to the primary section in order to cover the complete target lesion length.

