#### Inclusion:

[figure not shown]
Those subjects who sign and date the informed consent document, meet all of the study eligibility criteria, and are approved by the Independent Reviewer will be eligible for inclusion into the Valiant Evo International Clinical Trial. The subject will only be considered included when arterial access is established and an attempt to introduce the Valiant Evo Thoracic Stent Graft is made.

Included subjects will be documented on the Screening, Enrollment and Inclusion log and will be followed per the study protocol. Subjects who are enrolled and attempted to be implanted with the device but the Valiant Evo Thoracic Stent Graft could not be implanted during the procedure (treatment failure) will be followed through the 1 month follow-up per the study protocol and thereafter as per hospital standard of care. Serious Adverse Events will be collected for these subjects over the whole duration of the study. The reason for not including the subjects into the trial will be documented on the Screening, Enrollment and Inclusion log and will be documented on the screening eCRF.

The investigator will maintain a log of all subjects screened, enrolled, and included in the clinical study, assigning an identification code linked to their names, alternative subject identification or contact information.

As the point of enrollment is considered the point in time the subject signs and dates the Informed Consent Form, which is different from the point that the subject is actually included in the trial, more subjects will be enrolled in the trial than included. A 10 to 20% screen failure rate is expected. Therefore, approximately 57 subjects are expected to be enrolled in order to include 47 subjects.

\* The subject will only be considered included when arterial access has been established with an attempt to introduce the Valiant Evo thoracic stent graft.  
**Note:** A patient withdrawing informed consent stops the process on the date of withdrawal.

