**Table F-1: Post-Implantation Follow-Up Visit Schedule and Windows**

Follow-Up Visit	Window Start Day	Target Day	Window Close Day
1 Month (± 15 days)	15	30	45
12 Months (365 ±60 days)	305	365	425

At all required follow-up visits subjects will undergo the following assessments and procedures:

- Physical Examination
- Chest CT/MRI with contrast
- EQ-5D questionnaire
- Adverse event assessment

A CT/MRI with contrast acquired at discharge (or before day 15) due to medical necessity may be used to meet the 1-month follow-up visit CT/MRI requirement if a CT/MRI with contrast cannot be obtained within the 1-month follow-up window due to the subject's health status based upon physician discretion. If conversion to open repair is required during the follow-up period, then the subject will return for the 30-day follow-up visit, if applicable. Thereafter the subject will be followed per institutional standard of care and serious adverse events will be recorded in the eCRF until the total duration of the trial. At the end of the study the exit form should be completed.

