***F.6.2 Recording and reporting of Adverse Events***

Adverse Event (AE) information will be collected throughout the study and reported to Medtronic on the Adverse Event eCRF. All Adverse Events (except the ones listed in table F-3), regardless of relatedness or outcome, must be reported. The investigator is responsible for reporting all AE to Medtronic.

See the Adverse Event eCRF for the information to be reported for each Adverse Event.

For Adverse Events that require immediate reporting (see Table F-4), initial reporting may be done by phone, e-mail (contact details will be provided in the investigational site file), or on the eCRF with as much information as is available. In case the investigator requires information from the Sponsor in an emergency situation, the contact details for emergency situations are given in section F.6.7.

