- Aneurysm-Related Mortality within 365 days
- MDEs within 365 days
- All AEs within 365 days including:
 - MAEs
 - SAEs
- Secondary procedures within 365 days
- Loss of stent graft patency within 12 months based on imaging findings
- Endoleaks at 12 months based on imaging findings
- Stent graft migration at 12 months as compared to 1-month imaging
- Aneurysm expansion > 5mm at 12 months based on imaging findings relative to the 1-month visit

Secondary endpoints are to be assessed beyond 12 months. The following secondary endpoints are to be evaluated at 24, 36, 48, and 60 months:

- All-cause mortality
- Aneurysm-Related Mortality
- MDEs
- All AEs and SAEs
- Secondary procedures
- Loss of stent graft patency based on site reported imaging findings
- Endoleaks based on site reported imaging findings

- Stent graft migration as compared to 1-month imaging
- Aneurysm expansion > 5mm based on site reported imaging findings relative to the 1-month visit

Health-related quality of life outcomes are to be assessed at all scheduled follow-up visits using the EQ-5D questionnaire.

Stent graft migration will be determined by the core lab or site imaging case report from (CRF). Core lab assessment and site reported result will be analyzed separately. Aneurysm expansion will be calculated. When 1-month image is not available, the latest image taken prior to 1-month will be used for calculation.

Descriptive statistical analyses will be performed on secondary endpoints. No inferential statistical analysis is planned for secondary endpoints.

Non-image endpoints event rates such as mortality, secondary procedures, MAEs, SAEs, conversion to open surgery, and thoracic aortic aneurysm ruptures through 1 year will be calculated in the same way as the MDE rate, specified in Table 5. The event rates beyond 1 year through 5 years will be analyzed using Kaplan Meier method.

Imaging based Event Rate Calculation:

Unless otherwise specified, imaging assessment will be performed by site as well as the core lab. Assessments from the core lab will be the primary result for the PMA and PMA-s submissions and analyzed separately from those by site. Imaging based event rate will be calculated using statistical analysis windows as follows (Table 6):

Table 6: Imaging based Event Rate Calculation:

Event rate = m/n	At 1 Month	At 6 Months	At 12 Months

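### After 30 days the protocol names only SAEs for treatment failures and open conversions but elsewhere asks for all AEs to 12 months; if sites follow the narrower text, the descriptive 12-month MAE rate is slightly understated

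*Protocol*

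**What the plan says.** Three places in the protocol reduce event recording for subjects whose endovascular treatment failed.

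- F.1, for subjects in whom implantation was attempted but not achieved: protocol follow-up to the 1-month visit, then hospital care, and "Serious Adverse Events will be collected for these subjects over the whole duration of the study".
- F.2.2, for treatment failures: "These subjects will be followed for 30 days and thereafter per institutional standard of care. Serious adverse events will be recorded in the eCRF". For primary conversion to open repair: "then the subject will be followed for 30 days and thereafter per institutional standard of care", again with SAEs to the end of the trial. In both cases the exit form waits until the study ends.
- F.2.4, for conversion during follow-up: the 30-day visit if it still applies, and then "Thereafter the subject will be followed per institutional standard of care and serious adverse events will be recorded in the eCRF".

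Other places make no such exception.

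- C.5: "All subjects included will continue to be followed under this investigational protocol beyond the 30-day primary endpoint out to 12 months post-implantation".
- C.2.2.2 lists all AEs within 365 days, including MAEs and SAEs, as a 12-month endpoint.
- Table F-2 schedules an AE assessment at 12 months.
- F.6.2 says that all AEs other than those in Table F-3, "regardless of relatedness or outcome, must be reported".

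On the analysis side, protocol H.1 and SAP 7.1.3 analyse everyone in whom introduction of the graft was attempted, so these subjects are in the set. SAP 7.9 states that 1-year rates for non-imaging events, MAEs among them, "will be calculated in the same way as the MDE rate, specified in Table 5". In that table the rate is m/(m + k). At 365 days, k is the number of subjects with at least 305 days in study and no event. For a subject who has not exited, time in study runs to the data cut-off.

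**The concern.** Time in study and time under full AE collection are different things for these subjects, and Table 5 uses the first. A subject with a failed implant and no MAE on record stays open for SAE reporting, passes 305 days and enters k as event-free. Under the SAE-only text nobody was asked to record non-serious events for that subject after the 30-day follow-up, or after a later conversion.

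Several MAE definitions in L.2.2 do not require the event to be serious. New arrhythmia and paraparesis, defined as mild weakness of both legs, are examples. The 12-month MAE rate would then mix two levels of ascertainment. The lower level applies to subjects in whom the device or procedure failed, so any error favours the device. SAP Table 6 avoids this for imaging endpoints, because a subject without an event needs a readable image to be counted. Table 5 has no such safeguard.

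**Working it through.** **Step 1: how the texts combine.**

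| Question | F.1, F.2.2, F.2.4 | C.2.2.2, C.5, Table F-2, F.6.2 |
|---|---|---|
| Events recorded after 30 days (or later conversion) | SAEs named; others not mentioned | All AEs except Table F-3 |
| Who | Treatment failures, open conversions | All included subjects |
| Until | End of trial | 12 months |

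One site could follow the left column and another the right.

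**Step 2: the plan's own figure for the size of the failing group.** The documents state no MAE rate. The nearest figure is the expected number of 30-day primary-endpoint failures in C.7 and Table C-1: 3/47 = 6.4%. An exact binomial with n = 47 and p = 0.056 gives P(3 or fewer) = 0.7314 and P(6 or more) = 0.0463. Both match Table C-1.

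**Step 3: who is actually affected.** Those 3 failures cover the whole composite: access or deployment failure, device-related secondary procedure, device-related death, conversion and rupture. A secondary procedure does not in itself move a subject to SAE-only recording, and a subject who dies has no later events. Only treatment failures and conversions count, and their share is not given. I therefore assume x = 1 to 3 of 47. A conversion after Day 30 could add a subject, but with a shorter uncaptured period.

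**Step 4: size of the understatement.** Let q be the chance that an SAE-only subject has a non-serious MAE in the uncaptured period and no recorded MAE in the year. Neither document gives q; I assume 10 to 30%. With all N subjects in m + k, the understatement is x × q / N.

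- x = 1, N = 47: 1 × 0.10/47 = 0.2 points; 1 × 0.30/47 = 0.6 points.
- x = 3, N = 47: 3 × 0.10/47 = 0.6 points; 3 × 0.30/47 = 1.9 points.
- Ceiling for x = 3 (q = 100%): 3/47 = 6.4 points.
- Pooled N = 100, x = 1 to 3: 1 × 0.10/100 = 0.1 to 3 × 0.30/100 = 0.9 points.

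A subject who already has a recorded MAE is in m and contributes no error. The direction is therefore always downward.

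**Step 5: why dropping the event-free failures is no remedy.** Suppose, for illustration, 14 of 47 subjects have an MAE: 29.8%. Removing three event-free SAE-only subjects from k, while keeping in m any failures with an MAE, gives 14/44 = 31.8%. That raises the rate by 2.0 points, about as much as the largest bias in the range above, because exclusion now depends on the outcome.

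**The case against.** The strongest reply is that no passage forbids recording non-serious events in these subjects, and that F.6.2 requires all AEs without exception. That stands. A reader might infer that non-serious MAEs in this group cannot appear in the data. The documents support only a conflict whose effect depends on which text a site follows.

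A reader might also take 3 of 47 as the expected number affected, or use 5 of 47 to show a larger bias. The documents do not support either. Three is the expectation for the whole composite, and 5 or more failures has probability 1 − 0.8786 = 0.12 in Table C-1.

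The assumed risk can be challenged as well. Access-site hematoma and procedural bleeding above 750 cc occur around the procedure, when capture is full, so some of these subjects will already be in m. A creatinine rise counts only if levels are available, and Table F-2 schedules no laboratory test for anyone, so capture of that MAE is incomplete in implanted subjects too.

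Table 5 is extended by name to MAEs but not to all-AE rates. The AE tables in SAP 7.10 use subjects available at the start of each period. The SAP is written for the US trial and the pooled data, and the US protocol is not among the documents. Protocol H.1 does not state the m/(m + k) rule, although its analysis set also keeps these subjects in.

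Finally, the 12-month endpoints are descriptive, with no test or pass/fail rule. These points limit the size and reach of the problem. They do not resolve the conflict or the mismatch between time in study and time under AE collection.

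**Conclusion.** The protocol contradicts itself on AE recording after 30 days in treatment failures and conversions, and the passages must be reconciled. If the SAE-only text is followed, the 12-month MAE rate under SAP Table 5 is biased downward by about 0.2 to 1.9 percentage points. This rests on two assumptions that the documents do not supply: 1 to 3 affected subjects of 47, and a 10 to 30% risk of a first, non-serious MAE in the uncaptured period.

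A reader might infer that the trial's main safety result is compromised. It is not. The 30-day primary endpoint precedes the reduced capture, except after a conversion within 30 days, which is itself a primary-endpoint failure. MDEs go to the events committee throughout, and SAEs (hence serious MAEs) and deaths continue to be recorded. This is a small bias of known direction in a descriptive secondary endpoint, worth correcting because correction is cheap.

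**What to change.** **Preferred.** Align F.1, F.2.2 and F.2.4 with F.6.2, so that L.2.2 MAEs and other AEs are recorded through Day 365 for these subjects, using the contact that already serves SAE reporting. This concerns data recording only and changes nothing in how subjects are treated. The cost is a protocol amendment with the approvals in F.8.3 and a few more AE forms. Without a study visit, capture may remain somewhat lower than in implanted subjects.

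**If that is not adopted**, add a rule to SAP 7.9 for the 12-month MAE rate, in one of two forms:

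- Estimate the rate by Kaplan-Meier, which the SAP already uses for events beyond 1 year, and censor these subjects for MAE when full AE collection ends. This assumes that their later MAE risk resembles that of subjects still fully followed, which is doubtful after a failed procedure and should be stated.
- Show the rate with and without all SAE-only subjects, whether or not they had an event.

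Either way, footnote the reduced capture and the number of subjects concerned. Do not drop only the event-free failures from k. The SAP route costs a few sentences and one extra line in a table.

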### F.2.3 Hospital Discharge

The following assessments will be performed at hospital discharge and respective data will be collected on eCRFs:

- Adverse event assessment
- Duration of intensive care unit stay after index procedure (in hours)

### F.2.4 Follow-Up Visits and Procedures

Each subject will have required post-implantation follow-up visits at 30 days and 12 months. Follow-up visits and associated timeframe windows are summarized in Table F-1.

**Table F-1: Post-Implantation Follow-Up Visit Schedule and Windows**

Follow-Up Visit	Window Start Day	Target Day	Window Close Day
1 Month (± 15 days)	15	30	45
12 Months (365 ±60 days)	305	365	425

At all required follow-up visits subjects will undergo the following assessments and procedures:

- Physical Examination
- Chest CT/MRI with contrast
- EQ-5D questionnaire
- Adverse event assessment

A CT/MRI with contrast acquired at discharge (or before day 15) due to medical necessity may be used to meet the 1-month follow-up visit CT/MRI requirement if a CT/MRI with contrast cannot be obtained within the 1-month follow-up window due to the subject's health status based upon physician discretion. If conversion to open repair is required during the follow-up period, then the subject will return for the 30-day follow-up visit, if applicable. Thereafter the subject will be followed per institutional standard of care and serious adverse events will be recorded in the eCRF until the total duration of the trial. At the end of the study the exit form should be completed.

### F.3 Data collection requirements

Clinical data will be collected preoperatively to establish eligibility, at baseline, during the index procedure, throughout the hospital stay, and postoperatively at the required follow-up visits described in Section F.2. The data collection schedule is summarized in Table F-2. Imaging for baseline and follow-up assessments, as specified in Table F.2, will be sent to a Core Lab for analysis. In addition, any interim imaging of the stent graft region done within one year of implantation should be recorded on the interim image eCRF (e.g. 6-month imaging follow-up when performed as standard of care and/or when performed further to any issue observed at previous imaging follow-up). In case further analysis is needed, procedural and interim imaging exams are to be submitted to Core Lab.

Study data will be collected using electronic case report forms (eCRFs) as will be described in Section G.1. eCRFs should be electronically reviewed and approved by the clinical investigators. Medtronic monitors will perform source document verification of the eCRFs. The monitoring strategy will be defined in the monitoring plan.

For test equipment critical for assessing endpoints (e.g., CT scan, MRI, Transesophageal echography (TEE)) maintenance and calibrations will be monitored periodically.

It is expected that the Investigator enrolling the subject at the participating site where the implantation occurred will follow the subject during the course of the study. It is the responsibility of the Investigator to make sure that the subject is followed and that integrity and accuracy of the data is maintained.

**Table F-2: Data Collection Schedule**

DATA	Screening / Baseline	Index Procedure	Hospital Discharge	1-Mo. F/U (±15 days)	12-Mo. F/U (±60 days)
GENERAL					
Informed Consent	✓				
Inclusion Criteria/ Exclusion Criteria	✓				
Physical Examination	✓			✓	✓
Medical History	✓				
Current Health Status and Risk Factors	✓				
Device and Procedure Information		✓			
Pre-implant Adjunctive		✓			

DATA	Screening / Baseline	Index Procedure	Hospital Discharge	1-Mo. F/U (±15 days)	12-Mo. F/U (±60 days)
Procedures					
Hospital Discharge Information			✓		
Adverse event assessment	✓ a	✓	✓	✓	✓
EQ-5D questionnaire	✓			✓	✓
IMAGING					
CT/MRI with contrast b	✓			✓ c, d	✓ d
Angiography		✓ e			

a In case of screen failures, investigators will be requested to enter safety information in the eCRF from time point of enrolment until time point of screen failure

b CT evaluation may include “3-phase technique”, volume studies, 3-D reconstruction, or computer-aided measurements

c A CT/MRI with contrast acquired at discharge (or before Day 15) due to medical necessity may be used to meet the 1-month follow-up visit CT/MRI requirement if a CT/MRI with contrast cannot be obtained within the 1-month follow-up window due to the subject’s health status based upon physician discretion.

d MRI with contrast may be used for those patients experiencing renal failure or who are otherwise unable to undergo contrast-enhanced CT scan, with TEE being an additional option in the event of suboptimal MR imaging.

e Required to complete Procedure eCRF but not expected to be submitted to Medtronic or Core Lab unless further analysis is needed.

### F.4 Role of the sponsor’s representatives

Sponsor’s representatives may provide support as required for the clinical study, including technical support during implant. The sponsor’s representative is an experienced expert of device sizing, placement and the technical features of the device and will advise the implanting physician during the implant procedure if needed. The sponsor’s representative will not be involved actively during the placement and deployment of the Valiant Evo Thoracic Stent Graft System.

### F.5 Source documents

Investigators are required to maintain records of each subject’s case history, exposure to the device and clinical follow-ups. Source documents include subject’s hospital files (electronic or paper), images, programmer printouts, and device labels. For data that is not recorded as standard in the subject file, separate worksheets that will be marked as source data can be used. The investigator will clearly mark clinical records to indicate that the subject is enrolled in this clinical investigation. Note: there may be some country-specific requirements in this regard.

Investigators should maintain source documents to support the data recorded on the study case report forms. Complete medical (clinical and hospital) records include, but are not limited to, the following documentation:

- Medical history/physical condition of the subject before involvement in the study sufficient to verify clinical protocol entry criteria
- Description of device implantation procedure (material used, drugs administered during the procedure, device identification information and disposition, date, time, angiographic and clinical findings, etc.)

- Signed notes in the subject’s medical record on the enrollment day that identify and include: the subject’s date of enrollment/procedure date, the study sponsor, clinical site name, the subject number, and documentation and confirmation that the appropriate informed consent was obtained
- Dated and signed notes for each subject’s study visit
- Lab results
- All CT/MRI reports, etc.
- Dated printouts or reports of special assessments (ECG report, imaging report, etc.)
- Adverse event reporting and follow-up of the adverse events. Information in the medical chart should include at a minimum the following: event description, severity, seriousness, onset date, date site became aware of event, duration, relation to study device, treatment, and outcome of the adverse event
- Study subject’s condition upon completion of or withdrawal from the study

Where copies of the original source document as well as print outs of original electronic source documents are retained, these shall be signed and dated by a member of the investigation site team with a statement that it is a true reproduction of the original source document. In case subject contact has been performed by phone, the investigator needs to record as a minimum the date of contact in the subject’s hospital file. Furthermore, the reason for withdrawal and actions to trace lost to follow-up subjects should be documented in the medical records of the subjects.

The investigator(s) and study personnel must be accessible to the Medtronic field clinical support and the clinical study team. This accessibility is of particular importance for the completion and clarification of the data on the case report forms and regulatory responsibilities. Access to the subject records and other source data must be provided to study monitors, auditors and/or inspectors.

